Efficacy analyses in the secondary objectives specific to PsO and PsA will be conducted on the PsO with no active PsA and active PsA participants with at least 1 dose of study intervention and will be summarized with number of responders, response rate and its corresponding 95% confidence intervals (CIs) using normal approximation.

Number of Participants:

Approximately 250 participants (PsO: 150 participants; PsA: 100 participants) are planned to be enrolled into this study and, assuming discontinuations of approximately 10%, approximately 225 participants should complete the 24-week period of treatment.

Intervention Groups and Duration:

Treatment Group	Starting Dose W0	Dose W2-W10	Dose ^a W12-W20
Ixekizumab for 
 • PsO participants with no active PsA, and • PsA participants who meet criteria for moderate-to-severe PsO. 	Ixekizumab 80 mg 2 × SC (total of 160 mg)	Ixekizumab 80 mg SC Q2W at W2, 4, 6, 8, and 10	Ixekizumab 80 mg SC Q4W at W12, 16, and 20
Ixekizumab for PsA participants who do not meet criteria for moderate-to-severe PsO	Ixekizumab 80 mg 2 × SC (total of 160 mg)	Ixekizumab 80 mg SC Q4W at W4, 8, 12, 16, and 20.	

Abbreviations: PsA = psoriatic arthritis; PsO = psoriasis; Q2W = every 2 weeks; Q4W = every 4 weeks; SC = subcutaneous injection; W = week.

^a No dose is given at W24; therefore, W24 is not included in this table.

Note: When the dosing is scheduled at home (for PsO participants with no active PsA and PsA participants who meet criteria for moderate-to severe PsO: W2, W6, W10, W16, and W20; for PsA participants who do not meet criteria of moderate-to-severe PsO: W16 and W20), the participants or care givers will administer the provided ixekizumab prefilled syringes.

Data Monitoring Committee: No.

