In the UNCOVER studies, 32% to 42% of participants who received treatment with ixekizumab had complete resolution (PASI 100 or static Physician Global Assessment [sPGA] score of 0; versus none in the placebo group) of their PsO at Week 12; high levels of clinical response were maintained with continued exposure to ixekizumab 80 mg every 4 weeks (Q4W) through Week 60 with at least 50% of participants maintaining or attaining PASI 100 (Gordon et al. 2016). In the UNCOVER-2 and UNCOVER-3 studies, ixekizumab had greater efficacy than etanercept, a tumor necrosis factor inhibitor (TNFi); 40.5% of participants treated with ixekizumab 80 mg every 2 weeks (Q2W), compared with 5.3% of etanercept-treated participants, achieved PASI 100 after 12 weeks (Griffiths et al. 2015, Gordon et al. 2016). In a Phase 3 head-to-head study (IXORA-S), ixekizumab demonstrated superiority over the IL-12/23 antagonist ustekinumab in participants with moderate-to-severe PsO at Week 12; this trend was maintained through Week 52. The majority (76.5%) of ixekizumab-treated participants sustained a PASI 90 response through 1 year, and more than one-half of ixekizumab-treated participants (52.2%) had completely clear skin at Week 52. The corresponding rates for the ustekinumab-treated participants were 59.0% and 35.5%, respectively.

Studies of ixekizumab suggest ability to achieve PASI 90 (as shown in the VOYAGE studies). Ixekizumab also demonstrated a high percentage of participants achieving PASI 100, and a rapid onset of skin improvement after administration of ixekizumab (UNCOVER). Long-term evaluation of ixekizumab in a study, in which safety is tested, will provide important information to clinicians trying to determine long-term safety of drug class is the best for a given participant. The purpose of this study is to evaluate efficacy and safety, as well as rapidness of efficacy, of ixekizumab.

In both UNCOVER-2 and UNCOVER-3 studies combined, the most common ($\geq 2\%$ of all participants given ixekizumab) were nasopharyngitis, upper respiratory tract infection, injection-site reaction, injection-site erythema, injection-site pain, pruritus, headache, and arthralgia. Most treatment-emergent adverse events (TEAEs) were mild or moderate in severity. Serious adverse events (SAEs) were reported by $\leq 2\%$ of participants in each treatment group

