9.3.1 General Nonresponder Imputation for Clinical Response

Analysis of categorical efficacy and health outcomes variables will be assessed using a nonresponder imputation (NRI) method. Participants will be considered a nonresponder for the NRI analysis if they:

- do not meet the clinical response criteria (e.g., ACR20, PASI75, PASI90, PASI100, sPGA [0,1]);
- have missing clinical response data at a timepoint of interest (e.g., Week 12, Week 24);
- discontinue study treatment at any time prior to a timepoint of interest for any reason; or
- have no postbaseline observation.

The NRI may be applied at any time point specified for analysis.

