9.5 Statistical Analyses

9.5.1. General Considerations

Statistical analysis of this study will be the responsibility of Lilly.

Unless otherwise specified, continuous data will be summarized in terms of the mean, standard deviation, minimum, maximum, median, and number of observations. Categorical data will be summarized as frequency counts and percentages.

Baseline will be defined as the last non missing assessment recorded on or prior to the date of first injection for efficacy and health outcomes. In most cases, this will be the measure recorded at Week 0 (Visit 2). Change from baseline will be calculated as the visit value of interest minus the baseline value. For safety analyses using a baseline period, the baseline period is defined as the time from Visit 1 to the date/time of the first injection.

Any change to the data analysis methods described in the protocol will require an amendment ONLY if it changes a principal feature of the protocol. Any other change to the data analysis methods described in the protocol, and the justification for making the change, will be described in the clinical study report (CSR). Additional exploratory analyses of the data will be conducted, as deemed appropriate.

Complete details of the planned analyses will be documented in the SAP.

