9.5.3 Secondary Endpoint(s) Analysis

Endpoints Specific to Psoriasis (PsO) and Psoriatic Arthritis (PsA) Participants with 3% or More BSA of PsO

As a part of the secondary analyses, the following endpoints will be summarized (i) for the PsO indication and will be based on the PsO with no active PsA – mITT population, and (ii) for the active PsA indication and will be based on the active PsA – mITT population with BSA of PsO $\geq 3\%$ at baseline, unless otherwise specified:

Proportion of Participants with sPGA (0 or 1)

The proportion of participants achieving sPGA response of 0 or 1 at Week 12 will be summarized and the associated 95% confidence interval (CI) will be provided using normal approximation. Missing data will be imputed using the NRI method as defined in Section 9.3.1. Further details will be provided in SAP.

Proportion of Participants with PASI 75

The proportion of participants achieving a PASI 75 response at Week 12 will be summarized and the associated 95% CI will be provided using normal approximation. Missing data will be imputed using the NRI method as defined in Section 9.3.1. Further details will be provided in SAP.

Endpoints Specific to Psoriatic Arthritis (PsA)

As a part of the secondary analyses, the following endpoint will be summarized for the PsA indication and will be based on the active PsA-mITT population:

Percentage of Participants Achieving ACR20

The proportion of participants achieving a response of ACR20 at Week 24 (Visit 15) will be summarized and 95% CI will be provided using normal approximation. Further details will be provided in SAP.

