9.7 Sample Size Determination

No formal sample size calculation was done for this study.

Approximately, 250 participants (PsO: 150 participants and PsA: 100 participants) are planned to be enrolled into this study, and assuming discontinuations of approximately 10%, approximately 225 participants will be able to complete the 24-week period of treatment.

10 Supporting Documentation and Operational Considerations

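### Normal-approximation 95% intervals for PASI 75 and sPGA (0,1) fall short of 95% coverage and err upwards if response is high, mainly in the PsA subgroup with BSA of 3% or more

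*Protocol*

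**What the plan says.** Section 9.5.3 names the interval method for each skin endpoint at Week 12. The PASI 75 proportion is to be "summarized and the associated 95% CI will be provided using normal approximation", and sPGA (0,1) has the same provision. The Synopsis says the same of the secondary efficacy analyses: "response rate and its corresponding 95% confidence intervals (CIs) using normal approximation". No score, exact or continuity-corrected interval is named.

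The skin endpoints are summarised twice. The first summary is in the PsO mITT population without active PsA. The second is "for the active PsA indication and will be based on the active PsA – mITT population with BSA of PsO" of at least 3% at baseline. Section 9.7 gives the planned numbers by indication, "250 participants (PsO: 150 participants and PsA: 100 participants) are planned to be enrolled into this study", but the protocol does not say how many PsA participants will have BSA of 3% or more.

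Missing data are handled by nonresponder imputation (Section 9.3.1). Participants also count as nonresponders if they "discontinue study treatment at any time prior to a timepoint of interest for any reason". The denominator is therefore the full mITT group.

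**The concern.** The Wald interval is centred on the observed proportion and takes its width from the observed proportion. When the true rate is high, samples that happen to come out above it have a small estimated standard error and so a narrow interval, which then lies wholly above the truth. Samples that come out low have wider intervals and rarely miss. The result is coverage below 95%, with misses mostly on one side. In small groups the upper limit can also exceed 100%, and the interval has zero width when everyone responds. A score interval pulls its centre towards one half and largely avoids these faults.

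The study tests no hypothesis (Section 9.1) and has no formal sample size calculation (Section 9.7). The interval is therefore the only stated measure of precision for the two skin endpoints, and a lower bound that tends to be too favourable is the wrong way to err. The smaller PsA subgroup is the more exposed of the two.

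**Working it through.** **Inputs from the protocol**
- Planned enrolment is PsO 150 and PsA 100 (Section 9.7). The only arithmetic there reproduces: 150 + 100 = 250, and 250 × (1 − 0.10) = 225 completers. No figure is given for the precision of the response rates.
- The nearest response figure is in Section 2.2: "The majority (76.5%) of ixekizumab-treated participants sustained a PASI 90 response through 1 year". That is a different endpoint, time and study. It indicates that high PASI 75 rates are plausible, since every PASI 90 responder is also a PASI 75 responder, but it is not an estimate for this trial.

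**Assumptions**
- True rate 0.80 to 0.95, with lower ranges of 0.75 to 0.90 (nonresponder imputation lowers observed rates) and 0.60 to 0.80.
- PsA subgroup sizes of 50 and 30, besides the ceiling of about 100.

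**Formulas**, with p̂ = x/n and z = 1.96
- Wald: p̂ ± z·√(p̂(1−p̂)/n)
- Wilson: [p̂ + z²/(2n) ± z·√(p̂(1−p̂)/n + z²/(4n²))] / (1 + z²/n)
- Exact coverage at p: the sum of the binomial probabilities of all x whose interval contains p, averaged over 1,501 equally spaced values of p in each range, because coverage oscillates with n and p.

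**Worked examples at 90% observed**
- 135/150: the standard error is √(0.09/150) = 0.0245, so Wald is 0.90 ± 0.048, or 85.2% to 94.8%. The Wilson centre is (0.90 + 3.84/300)/(1 + 3.84/150) = 0.890 and its half-width is 0.048, giving 84.2% to 93.8%.
- 45/50: Wald 81.7% to 98.3%, Wilson 78.6% to 95.7%.
- 27/30: the standard error is √(0.09/30) = 0.0548, so Wald is 0.90 ± 0.107, or 79.3% to 100.7%. The Wilson centre is 0.855 and its half-width is 0.111, giving 74.4% to 96.5%.
- 30/30: Wald 100% to 100% (zero width), Wilson 88.6% to 100%.

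**Mean exact coverage of the nominal 95% interval**

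| n | Wald, p 0.80–0.95 | Wald, p 0.75–0.90 | Wald, p 0.60–0.80 |
|---|---|---|---|
| 150 | 93.7% | 94.2% | 94.6% |
| 100 | 93.1% | 93.8% | 94.4% |
| 50 | 91.3% | 92.6% | 93.7% |
| 30 | 89.4% | 90.7% | 92.8% |

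Over the two higher ranges, Wilson averages 95.1% to 95.6% and Clopper-Pearson 96.1% to 97.8%. Over 0.60 to 0.80, Wilson averages 95.0% to 95.1%.

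**Minimum coverage.** For p 0.80 to 0.95 at n=150, the lowest Wald coverage is 89.4% and the lowest Wilson coverage 93.2%. At n=30 they are 78.2% and 92.1%.

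**Direction of the misses (p 0.80 to 0.95).** The share of Wald misses in which the interval lies above the true rate is 78% at n=150, 89% at n=50 and 92% at n=30.

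**Upper Wald limit above 100%**

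| n | p = 0.80 | p = 0.90 |
|---|---|---|
| 150 | 0.0% | 0.01% |
| 100 | 0.0% | 0.8% |
| 50 | 0.6% | 25% |
| 30 | 12% | 60% |

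**ACR20.** Section 9.5.3 uses the same interval for ACR20. At n=100 and an assumed rate of 0.40 to 0.70, Wald averages 94.5% and Wilson 95.0%, and no upper limit passes 100%. The weakness is therefore specific to high rates.

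**The case against.** The strongest reply is about size. In the one skin group with a stated size, PsO at about 150, the average shortfall is 0.8 to 1.3 points and the limits move by about 1 point. The larger effects need both a small PsA subgroup and a high response in it, and the protocol documents neither. The 76.5% figure comes from moderate-to-severe psoriasis, whereas the PsA subgroup includes participants below that threshold who follow a different induction schedule. The overshoot depends strongly on the rate: at n=50 it falls from 25% at p=0.90 to 0.6% at p=0.80. Wilson also dips below 95% at some rates, and Clopper-Pearson is conservative. The intervals are descriptive, and the number of responders is reported, so a reader can recompute them.

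All of that stands, and it keeps the point minor. It does not remove it. Coverage stays below nominal, and Wilson stays closer to it, even for rates of 0.60 to 0.80.

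It can also be said that the protocol refers to the SAP for details, and that truncation at 100% or a continuity correction could appear there. But the protocol itself names the method, so the SAP would be adding detail to a choice already made. Truncation would remove the impossible limits without changing coverage. Wald is the usual reading of a normal approximation, although the protocol does not use that word.

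Finally, the observed proportion is itself unbiased. The upward lean belongs to the interval and not to the estimate.

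**Conclusion.** The concern holds in its conditional form. If Week 12 response is high, the specified interval covers less than 95% and errs upwards. For rates of 0.80 to 0.95 the average shortfall from 95% is 1.3 points at n=150, 1.9 at n=100, 3.7 at n=50 and 5.6 at n=30. The effect is small in the PsO group and material only if the PsA subgroup proves small. The result rests on the Wald reading, on the assumed response rates, and on the assumed subgroup sizes of 50 and 30. No decision or error rate depends on these intervals, so the change is worth making but not essential. ACR20 is not materially affected.

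**What to change.** In Section 9.5.3 and the Synopsis, replace the normal approximation with the Wilson score method for PASI 75 and sPGA (0,1), in both the PsO population and the PsA subgroup with BSA of 3% or more. Clopper-Pearson is the alternative if guaranteed coverage is preferred, at the price of wider intervals. Use the same method for ACR20 for consistency only.

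The cost is one phrase and a software option, with no extra data or patients. Limits become asymmetric about the observed rate. At 90% observed they move down by about 1 point at n=150 and by about 3 to 5 points at n=50 and n=30. Under Section 9.5.1 a change of analysis method "will require an amendment ONLY if it changes a principal feature of the protocol"; otherwise the change and its justification go in the clinical study report. Making it before results are seen avoids a change of method prompted by a limit above 100%.

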9.5.5 Safety Analyses

Safety will be assessed by summarizing AEs, laboratory analytes and vital signs. Abnormal physical examinations and concomitant medications will be listed. The overall duration of treatment exposure will also be summarized.

Safety data collected after study treatment discontinuation will be summarized separately.

The categorical safety measures will be summarized with incidence rates. The absolute and mean change from baseline of the continuous safety measures will be summarized by visits.

All safety analyses will be based on the safety population and will be summarized overall and by dosing regimen (Q2W/Q4W and Q4W/Q4W) as specified in [Table RHCZ.6.1](#).

Further details will be described in the SAP.

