1.1. Synopsis

Protocol Title: A 24-Week Multicenter, Open-Label, Single-Arm, Phase 4 Study to Evaluate the Safety of Ixekizumab in Patients with Moderate-to-Severe Plaque Psoriasis and/or Active Psoriatic Arthritis in India

Brief Title: A study to investigate the safety of ixekizumab in participants aged ≥ 18 years with moderate-to-severe plaque psoriasis and/or active psoriatic arthritis in India

Rationale:

The rationale for this post-approval Phase 4 study is to evaluate the safety and tolerability when ixekizumab is administered to participants in India with moderate-to-severe plaque psoriasis (PsO) and/or active psoriatic arthritis (PsA). This Phase 4 safety study is being performed as per conditional marketing approval from the Central Drugs Standard Control Organization (CDSCO), India. As per permission reference, Lilly has committed to conduct a Phase 4 study with ixekizumab in India. In addition to the established safety profile for adult PsO, and PsA, the safety and tolerability data in Indian population from this study are intended to:

- further support the known safety profile for ixekizumab in adult participants with PsO and PsA, and
- establish a better understanding of the benefit-risk relationship for ixekizumab in participants with PsO and PsA.

Objectives and Endpoints:

Objectives	Endpoints
Primary	

 To assess the type of adverse event (AE) and the proportion of Indian participants with PsO and participants with PsA reporting AEs and serious adverse events (SAEs) occurring within the duration of the study (24 weeks) after being started on ixekizumab 	
 AEs, including SAEs, treatment-emergent adverse events (TEAEs), and adverse events of special interest (AESIs) during the treatment period (Week 0 to Week 24)
Secondary	
Specific to Psoriasis Group	

 To evaluate percentage of participants achieving a $\geq 75\%$ improvement in Psoriasis Area and Severity Index (PASI) 	
 Proportion of participants who achieve the following PASI scores: PASI 75 (defined as 75% improvement from baseline in PASI) at Week 12

 To evaluate percentage of participants with a Static Physician Global Assessment (sPGA) (0,1) 	
 Proportion of participants with an sPGA psoriasis score of 0 or 1 (0, 1) at Week 12
Specific to Psoriatic Arthritis Group	

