2.3. Benefit/Risk Assessment

Ixekizumab has been demonstrated to be safe and effective for the treatment of participants with moderate-to-severe chronic PsO and/or active PsA. The risk profile for participants within this study is anticipated to be consistent with the known safety experience for ixekizumab.

More information about the known and expected benefits, risks, SAEs, and reasonably anticipated AEs of ixekizumab are found in the IB. Information on AEs expected to be related to the study intervention may be found in Section 6.2 (DCSI) of the IB. Information on SAEs that are expected in the study population independent of drug exposure and that will be assessed by the Sponsor in aggregate periodically during the course of the study, may be found in Section 5 (Effects in Humans) of the IB.

Taking into account the measures taken to minimize risk to participants participating in this study, the potential risks identified in association with ixekizumab are justified by the anticipated benefits that may be afforded to participants with PsO or PsA.

3. Objectives and Endpoints

Objectives	Endpoints
Primary	

 To assess the type of adverse event (AE) and the proportion of Indian participants with plaque psoriasis (PsO) and participants with psoriatic arthritis (PsA) reporting AEs and serious adverse events (SAEs) occurring within the duration of the study (24 weeks) after being started on ixekizumab. 	
 AEs including SAEs, treatment-emergent adverse events (TEAEs), and adverse events of special interest (AESIs) during the treatment periods (Week 0 to Week 24)
Secondary	
Specific to Psoriasis Group	

 To evaluate percentage of participants Achieving a $\geq 75\%$ Improvement in Psoriasis Area and Severity Index (PASI) 	
 Proportion of participants who achieve the following PASI scores: PASI 75 (defined as 75% improvement from baseline in PASI) at Week 12

 To evaluate percentage of participants with a Static Physician Global Assessment (sPGA) (0,1) 	
 Proportion of participants with an sPGA score of 0 or 1 (0, 1) at Week 12
Specific to Psoriatic Arthritis Group	

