6.1. Study Intervention(s) Administered

Table RHCZ.6.1. Treatment Regimens

Treatment Group	Starting Dose W0	Dose W2-W10	Dose ^a W12-W20
Ixekizumab for 
 • PsO participants with no active PsA • PsA participants who meet criteria for moderate-to-severe PsO 	Ixekizumab 80 mg × 2 SC (total of 160 mg)	Ixekizumab 80 mg SC Q2W at W2, 4, 6, 8, and 10	Ixekizumab 80 mg SC Q4W at W12, 16, and 20
Ixekizumab for PsA participants who do not meet criteria for moderate-to-severe PsO	Ixekizumab 80 mg × 2 SC (total of 160 mg)		Ixekizumab 80 mg SC Q4W at W4, 8, 12, 16, and 20

Abbreviations: PsA = psoriatic arthritis; PsO = psoriasis; Q2W = every 2 weeks; Q4W = every 4 weeks; SC = subcutaneous injection; W = week.

^a No dose is given at W24; therefore, W24 is not included in this table.

Note: When the dosing is scheduled at home (for PsO participants with no active PsA and PsA participants who meet criteria for moderate-to-severe PsO: W2, W6, W10, W16, and W20; for PsA participants who do not meet criteria for moderate-to-severe PsO: W16 and W20), the participants or care givers will administer the provided ixekizumab prefilled syringes.

The investigator or his/her designee is responsible for the following:

- explaining the correct method of dose administration to the participant or participant's caregiver;
- explaining the correct use of the investigational agent(s) to site personnel/legal representative;
- verifying those instructions are followed properly;
- maintaining accurate records of study intervention dispensing and collection; and
- returning all unused medication to Lilly or its designee at the end of the study

During study visits, the investigator or his/her designee will administer the ixekizumab prefilled syringes to the participant. When the dosing is scheduled at home, the participants or care givers will administer the provided ixekizumab prefilled syringes.

Note: In some cases, sites may destroy clinical trial material if during the investigator site selection, the evaluator has verified and documented that the site has appropriate facilities and written procedures for disposing of clinical trial materials.

Induction Dosing Period (Period 2) (Table RHCZ.6.2)

- At Week 0, a 160-mg starting dose of ixekizumab (two 80-mg injections), followed by ixekizumab 80 mg Q2W from Weeks 2 through 12 for PsO participants with no active PsA and PsA participants who meet criteria for moderate-to-severe PsO.

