8.1. Efficacy Assessments

The secondary endpoints for PsO group are:

- Proportion of participants who achieve the following PASI scores: PASI 75 (defined as 75% improvement from baseline in PASI) at Week 12
- Proportion of participants with an sPGA score of 0 or 1 (0, 1) at Week 12.

The secondary endpoints for PsA group are:

- Proportion of PsA participants achieving ACR20 at Week 24.

Exploratory endpoints include, but not limited to, DAS-28-CRP and ACR individual components.

For PsO participant who also meet active PsA definition, both PsA and PsO outcomes will be collected for that participant. Likewise, to fulfill the study objective, PsO outcomes will be collected among all the PsA participants with 3% or more BSA of PsO ([Table RHCZ.8.1](#)).

Table RHCZ.8.1. Efficacy Assessments

Assessments	PsO Participants with No Active PsA	PsA Participants with	
		≥3% BSA of PsO	<3% BSA of PsO
Clinician assessments	
 • PASI • Percentage of BSA - Psoriasis • sPGA • PGA Disease Activity VAS 	
 • TJC/SJC (68/66 joints) • PGA of Disease Activity VAS -Psoriasis • PGA of Disease Activity VAS - PsA • PASI • Percentage of BSA - Psoriasis • sPGA • DAS28 - CRP^a • ACR20/50/70^a 	
 • TJC/SJC (68/66 joints) • PGA of Disease Activity VAS - PsA • DAS28 - CRP^a • ACR20/50/70^a
Patient assessments	
 • Patient's Global Assessment of disease activity VAS - Psoriasis 	
 • HAQ-DI • PsA Pain assessment question included in HAQ-DI • Patient's Global Assessment of Disease Activity VAS - PsA • Patient's Global Assessment of Disease Activity VAS - Psoriasis 	
 • HAQ-DI • PsA Pain assessment question included in HAQ-DI • Patient's Global Assessment of Disease Activity VAS - PsA

Abbreviations: ACR20/50/70 = 20%/50%/70% improvement in American College of Rheumatology response criteria; BSA = body surface area;

CRP = C-reactive protein; DAS28 = Disease Activity Score-28; HAQ-DI = Health Assessment Questionnaire – Disability Index; PASI = Psoriasis Area and Severity Index; hs-CRP = high-sensitivity C-reactive protein; PGA = Physician's Global Assessment; PsA = psoriatic arthritis; PsO = plaque psoriasis; SJC = swollen joint count; sPGA = static Physician's Global Assessment; TJC = tender joint count, V = visit; VAS = visual analog scale.

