9.5.2 Primary Endpoint Analysis

The primary analysis, the number and percentage of participants in the safety population experiencing:

- TEAEs,
- TEAE by maximum severity,
- Death,
- SAEs,
- TEAE related to study treatment,
- AEs leading to treatment discontinuation, and
- TEAEs of special interest (hepatic, cytopenias, infections, allergic reactions/hypersensitivities, injection-site reactions, cerebrocardiovascular events, major adverse cerebrocardiovascular events [MACE], malignancies, depression, IBD, interstitial lung disease [ILD]).

These AEs, occurring within the duration of the study (24 weeks) after being started on Ixekizumab, will be summarized. For events that are gender-specific (as defined by the Medical Dictionary for Regulatory Activities [MedDRA]), the denominator and computation of percentage will include only participants from the given gender.

Refer to Section 9.5.5.1 for further details.

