9.5.5.1. Adverse Events

Adverse events are classified based upon MedDRA. A TEAE is defined as an event that first occurred or worsened in severity after baseline and on or prior to the date of the last visit within the treatment period. Both the date/time of the event and the date/time of the injection are considered when determining TEAEs. TEAEs will be assigned to the treatment period in which they first occurred or worsened. A follow-up emergent adverse event (FEAE) is defined as an event that first occurred or worsened in severity after the date of Week 24 (Visit 6) or the ETV. For events that are gender specific, the denominator and computation of the percentage will include only participants from the given gender.

A summary of AEs will be provided overall and by dosing regimen, including the number and percentage of participants who reported TEAEs, TEAEs by maximum severity, death, SAEs, TEAEs related to study intervention, discontinuations from the treatment due to an AE, and treatment-emergent AESIs: cytopenias, infections, injection-site reactions (ISRs), allergic reactions/hypersensitivities, cerebrocardiovascular events, MACE, malignancies, depression, IBD, ILD. TEAEs (all, by maximum severity, and possibly related to study intervention by the investigator), SAEs including deaths, AEs that lead to treatment discontinuation will be summarized by MedDRA system organ class (SOC) and PT.

In addition to general safety parameters, safety information on specific topics of AESIs will also be presented. Potential AESIs will be identified by a standardized MedDRA query (SMQ) or a Lilly defined MedDRA PT listing.

FEAEs, SAEs (including deaths), and AEs that lead to study discontinuation will be summarized.

9.5.5.2.Clinical Laboratory Tests

Laboratory assessments will be presented as mean changes from baseline and as incidence of treatment-emergent abnormal, high, or low laboratory values (see below). Shift tables will be presented for selected parameters.

- For categorical laboratory tests:
 - Treatment-emergent **abnormal** value = a change from normal at all baseline visits to abnormal at any time post baseline;
- For continuous laboratory tests:
 - Treatment-emergent **high** value = a change from a value less than or equal to the high limit at all baseline visits to a value greater than the high limit at any time postbaseline; and

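### The primary objective names AE and SAE proportions in PsO and in PsA participants, but safety is displayed only overall and by dosing regimen, so no planned column gives the PsA proportion

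*Protocol*

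**What the plan says.** The primary objective in the Synopsis (Section 1.1) is to assess, besides the type of AE, "the proportion of Indian participants with PsO and participants with PsA reporting AEs and serious adverse events (SAEs"). Section 3 has the same wording with the abbreviations spelled out. Enrolment is planned by indication in Section 9.7: "250 participants (PsO: 150 participants and PsA: 100 participants) are planned to be enrolled into this study".

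The analysis sections use other groups:

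- Section 9.5.2 defines the primary analysis as "the number and percentage of participants in the safety population experiencing" TEAEs, deaths, SAEs and so on, without a split, and refers to Section 9.5.5.1.
- Section 9.5.5.1 states: "A summary of AEs will be provided overall and by dosing regimen".
- Section 9.5.5 sets the same columns for everything: "All safety analyses will be based on the safety population and will be summarized overall and by dosing regimen (Q2W/Q4W and Q4W/Q4W").

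Table RHCZ.6.1 (Section 6.1) assigns Q2W/Q4W to PsO participants without active PsA and also to "PsA participants who meet criteria for moderate-to-severe PsO". Q4W/Q4W is for the remaining PsA participants. Efficacy is analysed by indication: Section 9.2 defines one population of PsO with no active PsA and another of active PsA on either regimen.

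**The concern.** Regimen does not stand in for indication here. One regimen column mixes the two diseases, and the other contains only the PsA participants with milder or no skin disease. The table that is meant to answer the primary objective would therefore have no PsA column.

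Two things are at stake. First, this is a safety study done as a condition of marketing approval, and its primary tables would not show one of the two proportions that the objective names. Second, Sections 1.1 and 2.1 say the data should clarify the benefit-risk relationship in PsO and PsA. ACR20 would be reported for all active PsA, and PASI 75 and sPGA (0,1) for PsO with no active PsA, with no AE column for either group. Benefit and risk would then be shown for differently composed sets of people.

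**Working it through.** **The plan's own figures.** 150 + 100 = 250, and 250 × (1 − 0.10) = 225, which is the number of completers stated in Section 9.7. The protocol plans no hypothesis test and no formal sample size calculation, so there is no power figure to reproduce.

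**Who is in each column** (Sections 4.1 and 6.1)

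| Participant | Regimen column | Efficacy population (Section 9.2) |
|---|---|---|
| PsO, no active PsA | Q2W/Q4W | PsO with no active PsA |
| Active PsA with moderate-to-severe PsO | Q2W/Q4W | Active PsA |
| Active PsA without moderate-to-severe PsO | Q4W/Q4W | Active PsA |

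The regimen and indication columns coincide only if the middle row is empty. The protocol expressly provides for that row in Table RHCZ.6.1, and in Section 8.1: "For PsO participant who also meet active PsA definition, both PsA and PsO outcomes will be collected for that participant".

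**Size of the mismatch.** The protocol gives neither the overlap share nor the enrolment target that a participant with both diseases counts towards. Both counting rules are shown, and the shares are assumptions.

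*Rule A: counted among the 100 PsA.* Let f be the share of them with moderate-to-severe PsO. Then n(Q2W/Q4W) = 150 + 100f, n(Q4W/Q4W) = 100(1 − f), and the PsA share of Q2W/Q4W is 100f / (150 + 100f).

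| f | Q2W/Q4W | Q4W/Q4W | PsA share of Q2W/Q4W |
|---|---|---|---|
| 0.2 | 170 | 80 | 20/170 = 11.8% |
| 0.3 | 180 | 70 | 30/180 = 16.7% |
| 0.5 | 200 | 50 | 50/200 = 25.0% |

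*Rule B: counted among the 150 PsO.* Let g be the share of them with active PsA. The columns stay at 150 and 100, the PsA total is 100 + 150g, and Q4W/Q4W covers 100 / (100 + 150g) of it.

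| g | PsA in Q2W/Q4W | Share of all PsA shown in Q4W/Q4W |
|---|---|---|
| 0.1 | 15 | 100/115 = 87.0% |
| 0.2 | 30 | 100/130 = 76.9% |
| 0.3 | 45 | 100/145 = 69.0% |

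**Can the PsA proportion be derived from the planned columns?** Take rule A with f = 0.5 and, purely as an illustration, an AE in 47.5% of Q2W/Q4W (95 of 200) and 50% of Q4W/Q4W (25 of 50). The 50 PsA participants in Q2W/Q4W could account for anywhere from 0 to 50 of the 95.

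- PsA proportion: between (0 + 25)/100 = 25% and (50 + 25)/100 = 75%.
- Proportion in PsO with no active PsA: between (95 − 50)/150 = 30% and 95/150 = 63.3%.

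The overall column is the sum of the other two, so it does not narrow either range.

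**Precision under rule A.** For an event seen in nobody, the one-sided 95% upper bound is 1 − 0.05^(1/n):

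- n = 100: 2.95%
- n = 80: 3.68%
- n = 50: 5.82%

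**Is a regimen split wrong in itself?** No. Planned injections in Table RHCZ.6.2 are 2 + 6 + 2 = 10 on Q2W/Q4W and 2 + 3 + 2 = 7 on Q4W/Q4W, so exposure differs and the split is informative. It just does not deliver the split that the objective names.

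**The case against.** The strongest case on the other side is that the objective uses the singular, one proportion over a joined population. In the same table the secondary objectives carry headings for the psoriasis and psoriatic arthritis groups, and the primary objective does not. Read that way, the overall column answers it. This reading is possible. It is less natural, because the sentence names the two groups separately and enrolment is planned by indication, and nowhere does the text state that a pooled proportion is meant.

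Next, Q2W/Q4W contains everyone with moderate-to-severe PsO, so it could serve as the PsO column. That stands if PsO is read to include people with active PsA. It still leaves no PsA column, and the group differs from the one used for PsO efficacy in Section 9.2.

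The SAP, which was not at hand, might add columns: Section 9.5.5 leaves further details to it and does not say that only these columns will be shown. That is true, but the protocol does not leave the layout open. It sets the columns for all safety analyses, and they do not match its own objective.

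Finally, the overlap shares are assumed, and the protocol sets no precision target. Both points are correct. The figures show a range and do not predict the shortfall, and the mismatch itself does not depend on them unless the overlap is zero.

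**Conclusion.** The concern holds. On the natural reading of the primary objective, the safety displays as specified leave it unanswered for PsA. For PsO they answer it only if participants with both diseases count as PsO. Under the assumed overlaps, Q4W/Q4W would show 80 to 50 of 100 PsA participants (rule A, 20% to 50% overlap) or 87% to 69% of all PsA participants (rule B, 10% to 30% overlap). The mismatch disappears only if no active PsA participant has moderate-to-severe PsO.

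This is a specification fault and not a loss of data: the split can be produced from what is collected. It should be fixed in advance, so that the grouping for the primary endpoint is not chosen after the results are seen.

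**What to change.** In Sections 9.5.2, 9.5.5 and 9.5.5.1, summarize the primary AE, SAE and AESI endpoints:

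- overall;
- by indication, classifying the safety population as in Section 9.2 (PsO with no active PsA; active PsA);
- by dosing regimen, with regimen also shown within active PsA.

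State that any dosed participant who fits neither indication, for example one enrolled inadvertently (Section 7.2.1), counts in the overall column. The essential minimum is the active PsA column; the PsO with no active PsA column lines safety up with efficacy.

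If a pooled estimate is what the sponsor intends, reword the primary objective in Sections 1.1 and 3 to say so.

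The cost is a few extra table columns or one reworded objective. It needs no new data, no more participants and no change to treatment.
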